4 STATISTICAL ANALYSES

4.1 GENERAL CONSIDERATIONS

In general, continuous data will be summarized using the number of observations available, mean, standard deviation (SD), median, minimum, and maximum. Categorical and ordinal data will be summarized using the count and percentage of participants.

The baseline value of efficacy parameters is defined as the last available value before randomization and prior to the first dose of study medication unless below eDiary data (WI-NRS, skin Pain-NRS and Sleep-NRS) score or otherwise specified.

The baseline for weekly average WI-NRS (skin Pain-NRS and Sleep-NRS) score is defined as the average of daily non-missing scores obtained during the 7 days prior to randomization.

The baseline value of the other parameters is defined as the last available value prior to the first dose of investigational medicinal product (IMP) if the participant is treated, or the last available value up to randomization if the participant is not exposed to IMP.

Observation period

The observation period will be divided into 4 segments:

- The **pre-treatment period** is defined as the period up to first IMP administration.
- The **treatment-emergent (TE) period** is defined as the period from the first IMP administration to the last IMP administration + 98 days. The treatment-emergent period includes the following 2 periods:
 - The **on-treatment period** is defined as the period from the first IMP administration to the last administration of the IMP + 14 days
 - The **residual treatment period** is defined as the period from the end of the on-treatment period to the end of the treatment-emergent period.
- The **post-treatment period** is defined as the period from the end of the treatment-emergent period.

The on-study observation period is defined as the time from start of intervention until the end of the study defined as the status date collected on e-CRF page “Completion of End of Study”.

4.2 PARTICIPANT DISPOSITIONS

The number (%) of participants included in each of the analysis populations listed in [Table 4](#) will be summarized.

Screen failures are defined as participants who consent to participate in the study but are not subsequently randomized. The number (%) of screen failures and reasons for screen failures will be provided in the screened population.

The number (%) of participants in the following categories will be provided:

- Randomized participants
- Randomized but not exposed participants
- Randomized and exposed participants
- Participants who completed the study treatment period as per protocol
- Participants who did not complete the study treatment period as per protocol and discontinued study treatment prior to Week 12 by main reason for permanent intervention discontinuation including due to COVID-19
- Participants who did not complete the study treatment period as per protocol and discontinued study treatment prior to Week 24 by main reason for permanent intervention discontinuation including due to COVID-19
- Participants who completed the study period as per protocol
- Participants who did not complete the study period as per protocol and discontinued study by main reason for study discontinuation including due to COVID-19.
- Vital status at last study contact

The number (%) of exposed and not randomized participants will also be summarized.

In addition, the number (%) of participants screened, screened-failed, randomized, with permanent intervention discontinuation and with early study discontinuation will be provided by country and site.

Protocol deviations

Critical and major protocol deviations (automatic or manual) will be summarized in the randomized population and according to COVID-19 impact (ie, deviations related to the COVID-19 pandemic and deviations not related to the COVID-19 pandemic). In addition, deviations potentially impacting the primary endpoint analysis will be summarized.

4.3 PRIMARY ENDPOINT(S) ANALYSIS

4.3.1 Definition of endpoint(s)

The primary endpoint for this study is the proportion of participants with improvement (reduction) in worst-itch numeric rating scale (WI-NRS) by ≥ 4 from baseline to Week 24.

WI-NRS is a patient-reported outcome (PRO) comprised of a single item rated on a scale from 0 (“No itch”) to 10 (“Worst imaginable itch”). Participants are asked to rate the intensity of their worst pruritus (itch) over the past 24 hours using this scale.

The weekly average WI-NRS score at each week, which is defined as the average of daily non-missing scores within the week window of each week (see [Section 5.4](#)), will be used for analyses.

For efficacy analysis, [Table 5](#) presents the prohibited and rescue medications/procedures which will be considered as intercurrent events if the last column indicates as “Yes” and therefore be handled in the estimands for endpoints defined in [Table 3](#).

Table 5 - Prohibited medications/procedures and rescue medications that impact efficacy

Medication/procedure	Comment	Data to be set as non-responder after taking medication in the main statistical analysis (Yes/No) ^a /Selection criteria
Prohibited medications/procedures		
Systemic immunosuppressive/immunomodulating drugs (eg, systemic corticosteroids, cyclosporine, mycophenolate-mofetil, interferon gamma, Janus kinase inhibitors, azathioprine, methotrexate, hydroxychloroquine, dapsone, sulfasalazine, colchicine, etc)	IMP to be discontinued	Yes (CDG ^b Immunosuppressant drugs Narrow and SDG ^b Corticosteroids Narrow)
Other monoclonal antibodies (that are biological response modifiers).	IMP to be discontinued	Yes (SDG ^b SDGMonoclonal antibodies Narrow)
Phototherapy, including tanning beds.	IMP to be discontinued	Yes (CMQ ^b HLT Phototherapies, CMQ ^b Tanning_single PT)
Naltrexone or other opioid antagonist	IMP to be discontinued	Yes (SDG ^b Analgesia producing opioids NARROW)
Gabapentin, pregabalin, and thalidomide	IMP to be discontinued	Yes (CDG ^b Gabapentin mono and multi ingredients, Pregabalin mono and multi ingredients, or Thalidomide mono and multi ingredients)
Paroxetine, fluvoxamine or other SSRIs.	No IMP discontinuation, see requirement in the footnote	Yes ^{c,d} (CDG ^b N06AB selective serotonin reuptake inhibitors)
SNRIs.	No IMP discontinuation, see requirement in the footnote	Yes ^{c,d} (CDG ^b serotonin and norepinephrine reuptake inhibitors)
Amitriptyline or other tricyclic or tetracyclic antidepressants	No IMP discontinuation, see requirement in the footnote	Yes ^{c,d} (CDG ^b N06AA non-selective monoamine reuptake inhibitors)
Intralesional corticosteroid injections and cryotherapy.	No IMP discontinuation	Yes ^d (CMQ ^b Injection_single pt, cryotherapy or skin cryotherapy PT)
Sedating antihistamine	No IMP discontinuation	Yes ^{d,e} (CDG ^b sedating antihistamines)
Non-sedating antihistamine if used specifically for the treatment of itch secondary to AD or PN	No IMP discontinuation	Yes ^{d,e} (CDG ^b non-sedating antihistamines)

Medication/procedure	Comment	Data to be set as non-responder after taking medication in the main statistical analysis (Yes/No) ^a /Selection criteria
Rescue medications		
Dermatological preparations of high potency or superpotent TCS and TCI	No IMP discontinuation	Yes ^d (CDG ^b calcineurin inhibitors and corticosteroids narrow, Ticked 'RESCUE THERAPY' in CRF page)
a When yes, the estimand for the intercurrent event handling strategy will be as follows: hypothetical for continuous endpoints, and composite for responder and time-to-event endpoints. When no, a treatment policy strategy will be applied. b CDG=company drug groupings, CMQ=company MedDRA query, SDG= Standardized drug groupings. c Only if the antidepressant is initiated during the study or its dose is increased from baseline provided that medication was taken at least 3 months prior to screening. d As per medical adjudication, see Section 5.7 for details. e Only if the medication is initiated at Week 12 or Week 24, or the dose is increased from Week 11 to Week 12 or from Week 23 to Week 24.		

Blinded review of prohibited/rescue treatment (medication or procedure) based on [Table 5](#) and a pre-specified algorithm ([Section 5.7](#)) will be implemented before database locks by considering the type of medication or procedure, indication, timing, frequency and the potential impact of the use of the prohibited medications/procedures and rescue medications.

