			To include the multicomponent endpoint in the hierarchy to address the health authority's feedback requesting assessment of this endpoint as another measure of treatment success.
			To explore the robustness of the estimate, and the inference thereof, with a different strategy for handling intercurrent events and missing data

SAP Version	Approval Date	Changes	Rationale
		Remove "selected" in the text including "selected prohibited and/or rescue medication"	Since a participant who takes any protocol specified prohibited medications/procedures and/or rescue medications is considered as a non-responder after medical adjudication/confirmation conducted in a blinded fashion, use of the word "selected" may be confusing.
		Add Appendix 7 back in Section 5.7	Add this medication/procedure adjudication algorithm back as it was inadvertently removed in SAP Version 2.
4.0	11-Nov-2021	
To promote the "proportion of participants with improvement (reduction) in worst-itch numeric rating scale (WI-NRS) by ≥ 4 from baseline to Week 24 as primary endpoint and to move the "proportion of participants with improvement (reduction) in WI-NRS by ≥ 4 from baseline to Week 12" to a secondary endpoint
 
To update hierarchical order in Section 4.6 by removing "Proportion of participants with improvement (reduction) in WI-NRS by ≥ 4 from baseline to Week 12", "Proportion of participants with IGA PN-S 0 or 1 score at Week 12" and "Change from baseline in Sleep-NRS to Week 24"
	
Based on the data from EFC16460, the treatment effect of dupilumab continued to improve over time through Week 24. Therefore, the Sponsor proposes to assess the proportion of participants with improvement (reduction) in WI-NRS by ≥ 4 at Week 24, which represents the effect more accurately and synchronizes the primary itch assessment with the primary lesion assessment. This is consistent with primary endpoint change in Protocol Amendment 3.
 
Updated power calculations performed using data from study EFC16460 showed low power for demonstrating statistical significance for each of these three endpoints. Accordingly, the hierarchical order was revised to remove these endpoints.

The first participant was randomized on 2020-01-02.

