The DLQI is a PRO developed to measure dermatology-specific HRQoL in adult participants. The instrument comprises 10 items assessing the impact of skin disease on participants' HRQoL over the previous week. The items cover symptoms, leisure activities, work/school or holiday time, personal relationships including intimate, the side effects of treatment, and emotional reactions to having a skin disease. It is a validated questionnaire used in clinical practice and clinical trials. Response scale is a 4-point Likert scale (0 = "not at all" and 3 = "very much") for nine items. The remaining one item about work/studying asks whether work/study has been prevented and then (if "No") to what degree the skin condition has been a problem at work/study; the item is rated on a 3-point Likert scale ("Not at all" to "A lot"). Overall scoring ranges from 0 to 30, with a high score indicative of a poor HRQoL.

Time-to-event secondary efficacy endpoint

Time to first onset of effect on pruritus defined as an improvement (reduction) in WI-NRS by ≥ 4 from baseline during the 24-week treatment period will be analyzed using the Cox proportional hazards model, including treatment, documented history of atopy (atopic or non-atopic), stable use of TCS/TCI (yes or no), region, and baseline anti-depressant use (yes or no). The hazards ratio, its 95% confidence interval and p-value will be reported. Kaplan-Meier curves will be also provided.

For time to first WI-NRS response (WI-NRS by ≥ 4 from baseline), participants who receive the prohibited medications and/or rescue medications (see [Table 5](#)), data prior to start of the medications will be used, but after medication start, the participants' data will not be used and they will be censored at Week 24 (ie, Day 172). For other participants, all available data up to Week 24 (ie, Day 172) including those collected during the off-treatment period will be used. Participants without events will be censored at Day 172 or their last WI-NRS assessment date if discontinued from the study, whichever is earlier.

Secondary efficacy endpoints that measure binary responses

Secondary efficacy endpoints that measure binary responses will be analyzed in the same fashion as the primary endpoint using primary statistical model.

Continuous secondary efficacy endpoints

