5.7 APPENDIX 7 MEDICATION/PROCEDURE ADJUDICATION ALGORITHM

Algorithm for determining whether treatment with following medications or procedures constitutes treatment failure resulting in setting data as non-responder after taking medication or undergoing procedure in the main statistical analysis

1. Not required to adjudicate post-baseline medications (WHODD-coded) or procedures (CMQ-coded) as these will be considered treatment failures if used at any time¹.
 - a) Always considered treatment failure
 - ATC2 = CORTICOSTEROIDS FOR SYSTEMIC USE
 - ATC2=IMMUNOSUPPRESSANTS (systemic, eg, oral or parenteral route)
 - Preferred Drug Name = Ciclosporin
 - Preferred Drug Name = Methotrexate
 - Preferred Drug Name = Mycophenolate sodium
 - Preferred Drug Name = Mycophenolic acid
 - Preferred Drug Name = Azathioprine
 - Preferred Drug Name = Gabapentin
 - Preferred Drug Name = Pregabalin
 - Preferred Drug Name = Thalidomide
 - Preferred Drug Name = Lenalidomide
 - Preferred Drug Name = Baricitinib
 - Preferred Drug Name = Ruxolitinib
 - Preferred Drug Name = Tofacitinib
 - Preferred Drug Name = AbrocitinibPreferred Drug Name = Delgocitinib
 - Preferred Drug Name = Nalbuphine
 - Preferred Drug Name = Naltrexone
 - Preferred Drug Name = Naloxone
 - Preferred Drug Name = Vixarelimab
 - Preferred Drug Name = Nemolizumab
 - Preferred Drug Name = Serlopitant
 - Preferred Drug Name = Aprepitant
 - CMQb HLT Phototherapies
 - CMQ Tanning_single PT
 - b) Never considered treatment failure:
 - ATC2 = EMOLLIENTS AND PROTECTIVES

- ATC2 = GENERAL NUTRIENTS
- ATC2 = VITAMINS
- ATC2 = ANTIVIRALS FOR SYSTEMIC USE
- ATC2 = ANTIFUNGALS FOR DERMATOLOGICAL USE
- ATC2 = ANTISEPTICS AND DISINFECTANTS
- ATC2 = ANTIBIOTICS AND CHEMOTHERAPEUTICS FOR DERMATOLOGICAL USE
- ATC2 = ANTI-ACNE PREPARATIONS, excluding D10AA Corticosteroids, combinations for treatment of acne
- ATC2 = OPHTHALMOLOGICALS
- ATC1 = ANTIINFECTIVES FOR SYSTEMIC USE, excluding D07C Corticosteroids, combinations with antibiotics
- ATC1 = BLOOD AND BLOOD FORMING ORGANS
- ATC1 = ALIMENTARY TRACT AND METABOLISM
- ATC1 = MUSCULO-SKELETAL SYSTEM, excluding M01BA Antiinflammatory/antirheumatic agents in combination with corticosteroids
- ATC2 = COUGH AND COLD PREPARATIONS
- ATC2 = PSYCHOLEPTICS, excluding N05BB Diphenylmethane derivatives and N05C HYPNOTICS AND SEDATIVES

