¹ A blinded review of all post-baseline medications or procedures to adjudicate whether treatment constitutes treatment failure, based on medical judgment, may be performed in addition. A listing of treatments or procedures classified as treatment failure in a manner inconsistent with the classification under #1 will be provided, along with supporting rationale.

2. Require to adjudicate medications or procedures that may constitute treatment failure

- All other medications and procedures listed in the protocol and [Table 5](#) of the SAP (not noted in 1. above) given for indications consistent with PN²
- Considerations in determining treatment failure include the criteria already set forth in [Table 5](#) of the SAP in addition to the type of medication or procedure, indication, dose, route of administration, timing, frequency and the potential impact of the use of the prohibited medications/procedures and rescue medications on the primary and key secondary efficacy endpoints.

2 Below is a list of indications consistent with PN based on PT level from concomitant medication/procedure data using MedDRA dictionary

System Organ Class	High Level Term	Preferred Term	Preferred Term Code
Skin and subcutaneous tissue disorders	Dermatitis and eczema	Neurodermatitis	10029263
Infections and infestations	Bacterial infections NEC	Eczema impetiginous	10051890
Infections and infestations	Skin structures and soft tissue infections	Dermatitis infected	10012470
Infections and infestations	Skin structures and soft tissue infections	Eczema infected	10014199
Skin and subcutaneous tissue disorders	Dermatitis and eczema	Dermatitis	10012431
Skin and subcutaneous tissue disorders	Dermatitis and eczema	Dermatitis atopic	10012438
Skin and subcutaneous tissue disorders	Dermatitis and eczema	Eczema	10014184

Signature Page for VV-CLIN-0602722 v5.0
efc16459-16-1-9-sap

Approve & eSign

Approve & eSign

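### SAP Table 5 selects opioid antagonists through a grouping named for opioid analgesics, and so conflicts with its own row label, Protocol 6.5 and SAP Section 5.7

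*SAP*

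**What the plan says.** SAP Section 4.3.1 states that a Table 5 row marked Yes in the last column is an intercurrent event under the estimands of Table 3. That column also holds the selection criterion. The row for "Naltrexone or other opioid antagonist" is marked Yes, and its criterion is the standardized drug grouping "Analgesia producing opioids NARROW". Protocol 6.5 and SAP Section 5.3 prohibit the same class as the row label. Neither lists opioid analgesics.

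Seven of the twelve rows in Table 5 carry footnote d ("As per medical adjudication, see Section 5.7 for details"). The opioid row does not.

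The adjudication algorithm in SAP Section 5.7 has two parts. Item 1 lists drugs and procedures that need no adjudication, "as these will be considered treatment failures if used at any time". That list includes naltrexone, nalbuphine and "Preferred Drug Name = Naloxone", and no opioid-analgesic class. Item 2 sends the other medications in the protocol and Table 5 to adjudication when they are given for an indication consistent with PN.

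**The concern.** The selector names, in effect, the opposite pharmacological class to the row it serves. Read literally, it errs in both directions: it picks up participants who took an opioid for pain, which is not a prohibited medication, and it does not pick up antagonists.

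The row feeds almost every efficacy analysis. Section 4.3.2 makes users of Table 5 medications non-responders for the primary endpoint, and Section 4.4.1.2 carries the same estimand to the key secondary endpoints. For the time-to-event endpoint, after the medication starts the participants' "data will not be used and they will be censored at Week 24" (Section 4.4.2). For continuous endpoints, later values are set to missing and the worst earlier post-baseline value is used. Section 4.8.3 censors total IgE on the same table. If Table 5 and Section 5.7 classify one participant differently, the primary outcome of that participant is not fixed in advance.

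**Working it through.** **Comparison of the rules**

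| Source | Opioid antagonist | Opioid analgesic given for pain |
|---|---|---|
| Protocol 6.5; SAP 5.3 | Prohibited | Not listed |
| Table 5, row label | Intercurrent event | Not covered |
| Table 5, selector (by its name) | Not found | Intercurrent event, no adjudication footnote |
| SAP 5.7, item 1 | Naltrexone, naloxone, nalbuphine: automatic failure | Not on the always list, nor among the 15 ATC groups on the never list |
| SAP 5.7, item 2 | Other antagonists: adjudicated if given for a PN-type indication | Not reached: none of the seven listed preferred terms is pain or injury |

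Item 2 applies only to medications "not noted in 1. above) given for indications consistent with PN", so an opioid for a fracture or an operation falls outside it. The table also shows a second gap: an antagonist other than the three named drugs is an unconditional event by the row label, but under Section 5.7 only when the indication fits.

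Exclusion criterion E 02 names opioids as a possible cause of PN, so the protocol itself does not treat opioids and their antagonists as one class. Table 14 in SAP Section 5.6 lists conjunctivitis and immunoglobulin terms only, so the membership of the opioid grouping cannot be checked.

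**Size, hypothetical worst case**

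The plan's own power figure cannot be reproduced, because the assumed response rates are redacted, and the documents give no rate of opioid use. The inputs are:

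- From the documents: 56 per arm for 90% power, two-sided Fisher exact test at 0.05, 75 per arm randomized, 15% dropout, missing data counted as non-response.
- Assumed: placebo response from 8% to 30%, each paired with the dupilumab rate that gives 90% power at 56 per arm (33.5% to 62.0%); an opioid-user share of 5% or 10% in both arms; every user reclassified.

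Analysed rate = p × 0.85 × (1 − share), with 75 per arm. Expected dupilumab responders lost = 75 × p × 0.85 × share.

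| Placebo / dupilumab | Power at 0% | at 5% | at 10% | Dupilumab responders lost at 5% / 10% |
|---|---|---|---|---|
| 8% / 33.5% | 93.0% | 91.3% | 89.4% | 1.1 / 2.1 |
| 10% / 36.6% | 92.6% | 90.8% | 88.6% | 1.2 / 2.3 |
| 20% / 50.1% | 91.4% | 89.3% | 86.7% | 1.6 / 3.2 |
| 30% / 62.0% | 91.5% | 88.7% | 85.4% | 2.0 / 4.0 |

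For example, 75 × 0.62 × 0.85 × 0.05 = 2.0. The loss of power is about 1.7 to 2.8 points at 5% and 3.6 to 6.1 points at 10%. With a 2% share, the same formulas give 0.4 to 0.8 responders lost and about 1 point of power or less. If Section 5.7 governs, opioids given for pain are not reclassified and the loss is zero.

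**The case against.** The strongest reply is that the selector is only a search string and that classification happens elsewhere. Directly below Table 5, Section 4.3.1 provides for blinded review before database locks that considers type of medication and indication, and it does not confine that review to rows with footnote d. The version history says that a participant who takes a protocol-specified prohibited medication "is considered as a non-responder after medical adjudication/confirmation conducted in a blinded fashion". Section 5.7 presents itself as the algorithm that decides treatment failure. Other selectors also look broad: the row for systemic immunosuppressive drugs uses a corticosteroid grouping with no route stated. Naltrexone and naloxone are caught by name in any case, and the grouping may hold drugs that its name does not suggest.

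Much of this stands. It makes it likely that an opioid given for pain would in the end not count as failure, and it is why the expected effect is small. It does not remove the conflict. The review is based on both Table 5 and Section 5.7, so it inherits their disagreement. Sections 4.3.2, 4.4.2 and 4.8.3 cite Table 5, not Section 5.7, when they state the handling rule. The Table 5 column is headed as the rule for setting data to non-response, not as a retrieval step. Even if the grouping does contain antagonists, its name implies analgesics as well, so it would still select more than Protocol 6.5 prohibits. Nalbuphine, which is not a pure antagonist, makes the contrast with Section 5.7 a little less sharp, but it does not bring in the analgesic class.

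**Conclusion.** The concern holds. The selector contradicts its row label, Protocol 6.5 and the preferred-name list in Section 5.7, and the SAP does not say which of Table 5 and Section 5.7 prevails. This should be fixed because it is an operative part of the primary estimand, even though the effect on the result is probably small. That effect lies between zero, if Section 5.7 governs, and the worst-case figures above, which rest on assumed response rates and assumed opioid use. Equal reclassification in both arms shrinks the treatment difference; unequal use between arms could bias it. The one thing the documents cannot settle is the membership of the grouping, so the contradiction is established from its name.

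**What to change.** Before database lock:

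1. Replace the selector in the Table 5 opioid row with one that matches the row label and Section 5.7: either an opioid-antagonist grouping, or the Section 5.7 preferred names (naltrexone, naloxone, nalbuphine) plus other opioid antagonists.
2. Reconcile Table 5 with Section 5.7 so that the SAP says explicitly whether an opioid analgesic is an intercurrent event, and how antagonists not named in Section 5.7 are handled.
3. Add one sentence stating which of Table 5 and Section 5.7 governs when they differ.

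The cost is one table cell, a short clarification and the matching programming. No new data are needed and there is no material downside. The change concerns the analysis rule only, not which medications participants may receive.
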